1.0 Definitions

Definitions

Eligible patients: All patients who meet all inclusion criteria and no exclusion criterion.

Consented participants: All eligible patients who have completed the consenting process.

Enrolled participants: All participants who have been randomized.

Intention-to-treat (ITT) Population: All enrolled participants, regardless of whether they received study drug or completed study procedures. This is the primary analysis population.

Study day: The calendar day of enrollment (randomization) is study day zero. The next day is study day one, and so on.

Assessment day: This corresponds to the survey instrument (day one survey is given on assessment day one).

Study Drug Discontinuation: Participant chooses to discontinue study drug, for any reason. Other study procedures may continue as decision of participant.

Study withdrawal: Participant discontinues study drug and does not wish to provide further study samples or data. Data recorded up to the time of withdrawal will be included in the study analysis.

Serious unexpected suspected adverse event (SUSAR): A serious adverse event or drug reaction that is unexpected and believed related to participation in study.

UTAH One (Understanding Treatment And Health in the Ongoing coroNa Epidemic): A Hydrochloroquine Outpatient Study

2.0 Study Summary

2.1 **Study title:** Hydroxychloroquine for Outpatients with Confirmed COVID-19 (HCQ Trial).

2.2 **Study objectives:** Assess the efficacy and safety of hydroxychloroquine (HCQ) for reduction of viral shedding and hospitalization in outpatients with confirmed COVID-19.

2.3 **Study hypothesis:** Hydroxychloroquine is effective in reducing viral shedding and need for hospitalization in outpatients with confirmed COVID-19.

2.4 **Study design:** Phase 2, prospective, open-label, parallel group, randomized controlled trial

2.5 Inclusion criteria

Inclusion Criteria for Randomized Group:

- Patient age ≥ 18 years, competent to provide consent
- Within 72 hours of positive nucleic acid test for SARS-CoV-2

Inclusion Criteria for Household Contact Group:

- Individual age ≥ 18 living in the same house as someone diagnosed with COVID, competent to provide consent

2.6 Exclusion criteria

- Patient already prescribed chloroquine or hydroxychloroquine
- Allergy to hydroxychloroquine
- History of bone marrow or solid organ transplant
- Known G6PD deficiency
- Chronic hemodialysis, peritoneal dialysis, continuous renal replacement therapy or Glomerular Filtration Rate $< 20\text{ml/min}/1.73\text{m}^2$
- Known liver disease (e.g. Child Pugh score $\geq B$ or AST >2 times upper limit)
- Psoriasis
- Porphyria
- Known cardiac conduction delay (QTc $> 500\text{mSec}$)
- Concomitant use of digitalis, flecainide, amiodarone, procainamide, propafenone, or any other prescription medication known to prolong the QT interval
- Seizure disorder
- Prisoner
- Weight $< 45\text{kg}$
- Inability to follow-up – no cell phone or no address or not Spanish or English speaking
- Receipt of any experimental treatment for SARS-CoV-2 (off-label, compassionate use, or trial related) within the 30 days prior to the time of the screening evaluation
- Patient or another member of patient's household has been already enrolled in this study.
- History of ventricular arrhythmia

2.7 **Sample size:** The study will enroll up to approximately 200 participants in each arm (total 400 participants).

2.8 **Primary Endpoint:**

UTAH One (Understanding Treatment And Health in the Ongoing coroNa Epidemic): A Hydrochloroquine Outpatient Study

- Duration of viral shedding, as defined by time from randomization to the first of two consecutive negative swabs, measured on days 1 - 14.

2.9 Interim Monitoring:

Formal safety review by Data Safety Monitoring Board (DSMB) after 100, 200, and 300 subjects enrolled. No interim efficacy analyses or monitoring.

3.0 STUDY DESCRIPTION

3.1 Background

COVID-19 is a pandemic illness caused by the SARS-CoV-2 virus and has a high mortality among hospitalized patients despite a benign course in the large majority of patients infected. Limited data are available from small outpatient studies and have not shown efficacy in preventing hospitalization. Hydroxychloroquine (HCQ) and chloroquine have antiviral and immune-modulating effects¹, but there are no data concerning their efficacy in reducing viral load and shedding in outpatients.

3.1.1 Evidence supporting possible efficacy for hydroxychloroquine.

In cell models, chloroquine both interferes with terminal glycosylation of the ACE2 receptor (the cell surface receptor by which SARS-CoV-2 enters human cells) and increases endosomal pH, which interferes (at least *in vitro*) with a crucial step in viral replication.^{1,2} HCQ is 5x more potent than chloroquine in a Vero cell model of SARS-CoV-2 infection.³ In independent experiments, chloroquine has confirmed *in vitro* activity against SARS-CoV-2.⁴ Additionally, HCQ has *in vitro* efficacy against SARS-CoV-1.⁵ According to news releases, an as-yet-unpublished set of case series in China (N reportedly 120) suggests the possibility of rapid viral clearance and low rates of progression to critical illness. In addition to *in vitro* anti-viral effects chloroquine and HCQ appear to have immune-modulatory effects, especially via suppression of release of TNF and IL6, especially in macrophages.^{1,7-10}

3.1.2 Evidence against efficacy for hydroxychloroquine.

Chloroquine and HCQ have been promoted as extremely broad anti-infective agents for decades. The reported effects include suppression of fungi, atypical bacteria, and viruses. Other than the effects on ACE2 glycosylation, the mechanisms invoked as evidence for efficacy against SARS-CoV-2 have also been invoked for a wide range of viruses. However, when chloroquine and HCQ have been studied in humans, neither agent has demonstrated consistent efficacy in clinical trials, including in HIV, influenza, hepatitis, and Dengue.¹¹ In one trial, chloroquine resulted in increased viral replication in Chikungunya virus [Roques et al, *Viruses* 2018 May 17;10(5)] while in another hydroxychloroquine was associated with increased HIV viral load [Paton et al, *JAMA* 2012 Jul 25;308(4):353]. Expert opinion advises against HCQ for MERS, another serious coronavirus.¹² An underpowered (n=30) study of HCQ in COVID-19 recently published in China did not demonstrate any clinical benefit [Chen et al, *J Zhejiang University*, 2020 March 9]. The long history of clinical failure despite *in vitro* anti-viral activity suggests a low probability of efficacy.

3.1.3. Rationale for Trial

There is significant publicity concerning the potential use of HCQ in this pandemic, and many patients are seeking access to this unproven therapy. The ANZICS guidelines emphasize that novel treatments should be administered within clinical trials; the Surviving Sepsis Campaign guidelines (<http://bit.ly/SSCCOVID-19>) also affirm the lack of evidence to support the clinical use

UTAH One (Understanding Treatment And Health in the Ongoing coroNa Epidemic): A Hydrochloroquine Outpatient Study

of (hydroxy)chloroquine. WHO guidance (<https://apps.who.int/iris/bitstream/handle/10665/331446/WHO-2019-nCoV-clinical-2020.4-eng.pdf>) also strongly affirms that “investigational anti-COVID-19 therapeutics should be done under ethically approved, randomized, controlled trials.” The evidence thus strongly favors equipoise.¹³

3.2 Study Design

Phase 2, prospective, placebo-controlled, parallel group, randomized trial

3.3 Study Objective

A novel coronavirus, SARS-CoV-2, is responsible for a rapidly spreading pandemic that has reached 160 countries, infecting over 500,000 individuals and killing more than 24,000 people. SARS-CoV-2 causes an acute and potentially lethal respiratory illness, known as COVID-19, that is threatening to overwhelm health care systems due to a dramatic surge in hospitalized and critically ill patients. Patients hospitalized with COVID-19 typically have been symptomatic for 5-7 days prior to admission, indicating that there is a window during which an effective intervention could significantly alter the course of illness, lessen disease spread, and alleviate the stress on hospital resources.

There is no known treatment for COVID-19, though in vitro and one poorly controlled study have identified a potential antiviral activity for HCQ. The rationale for this clinical trial is to measure the efficacy and safety of hydroxychloroquine for reducing viral load and shedding in adult outpatients with confirmed COVID-19.

3.4 Study Hypothesis

HCQ is effective in reducing viral shedding in outpatients with confirmed COVID-19.

3.5 Primary endpoint

- Duration of viral shedding, as defined by time from randomization to the first of two consecutive negative swabs, measured on days 1 - 14.

3.6 Secondary endpoints

- Average level of select COVID-19-attributable symptoms
- Hospitalization within 14 days of enrollment.
- Persistence of viral shedding on day 28.
- Adult household contact viral acquisition

4.0 Study population

Ambulatory patients for whom SARS-CoV-2 testing is obtained at University of Utah testing sites after evaluation via telehealth services or by providers in University affiliated clinical facilities.

4.1 Screening

Patients undergoing testing for SARS-CoV-2 will be informed of this actively enrolling interventional trial and provided with informed consent documentation (hard copy or electronic) at the time of testing. Patients will be asked if they would be interested in considering trial participation if their test is positive. Investigators will monitor test results of individuals who indicate interest in the trial and contact those with positive tests to verify eligibility and provide remote informed consent by telephone, electronic consent, or videoconference. The consenting

UTAH One (Understanding Treatment And Health in the Ongoing coroNa Epidemic): A Hydrochloroquine Outpatient Study

process will be performed via a consenting mechanism that confirms the identity of the patient, provides access to the consent form, and obtains a signature to complete documentation, without requiring physical proximity of research staff and the study subject. The informed consent documentation will include HIPAA authorization for access to the medical record.

4.2 Inclusion and Exclusion Criteria

See sections 2.5 and 2.6.

5.0 Study Procedures

5.1 Intake medication review.

Prior to randomization, study personnel and/or clinical pharmacists will review medications being prescribed for patients on study to confirm eligibility. Study personnel will advise patients to contact the study team if any new medications are prescribed during the 5 day treatment course so that the medication may be reviewed for risk of prolonging QTc.

5.2 Cardiac review.

Prior to randomization, study personnel will review if patient has electrocardiograms (ECG) and will verify that prolongation of QTc has not been diagnosed clinically or on ECG.

5.3 Randomization.

After obtaining informed consent, participants will be randomized using variable block sizes stratified by patient age group (age ≤ 44, 45-59, 60-74, 75+ years). The randomization system at the Data Coordinating Center will require entry of patient initials, date of birth and sex. This will assure that patients do not attempt to enroll multiple times in order to secure active drug.

5.4 Study drug.

This is an open label, variable block randomized placebo controlled trial. If a participant is admitted to the hospital at any time during the active treatment period, the clinical team will decide whether or not to continue study drug treatment during hospitalization.

Participants randomized to the HCQ arm will receive HCQ 400mg po BID x 1 day, then 200mg po BID x 4 days³. The drug dose (2.4 gm over 5 days) falls at the lower end of doses proposed in various international trials, but it has proven in vitro efficacy, with a ratio of lung tissue trough concentrations to the EC50 (effective concentration to suppress 50% of viral activity) of >20.³

Those randomized to placebo will receive a placebo to be taken on the same schedule.

5.5 Study Assessments.

Coordinators will obtain baseline information at the time of randomization. This will include review of all medications being prescribed for patients on study. Study personnel will advise patients to contact the study team if any new medications are prescribed during the 5 day treatment course so that the medication may be reviewed for risk of prolonging QTc, or having a drug interaction with HCQ (see Appendix 3).

Daily assessments (assessment days 1 through 15) will include review for hospitalization and current symptoms. Daily assessments will also explicitly solicit occurrence of rash, symptomatic hypoglycemia, seizure, oxygen supplementation, nausea, vomiting, and impaired vision. Quality of life assessments will be made at baseline, day 28 - 2 days/+2 weeks, and six months - 1

UTAH One (Understanding Treatment And Health in the Ongoing coroNa Epidemic): A Hydrochloroquine Outpatient Study

week/+2 months, using the EQ-5D-5L, PHQ-9, GAD 7, and PLC 5. If the six-month survey is missed during the above outlined window, the study team may attempt to collect it for up to a year following the six-month timepoint.

Participants will be taught how to perform self-collection of oral swabs for SARS-CoV-2 on assessment days 1 – 14 and 28 +/- 2 (considering day 1 as day of study drug delivery). Oral swabs will not be required during hospitalizations, but patients will be asked to provide a swab on the day following discharge from the hospital, even if this occurs after day 28. These will be refrigerated after collection and collected by a courier associated with the study for transport to the central laboratory (ARUP) for testing. Training will be provided with written instructions, video, and discussion with the research coordinators.

Phlebotomy will be performed at day 1, day 7 (+/-2 day), day 28 (+/-2 day) and 6 months- 1 week/+2 months. This will require personal protective equipment (PPE) for the phlebotomy-certified research staff. Note that the 6 months blood draw is being added mid-study, after subjects have been enrolled. Therefore, already enrolled participants will be notified of the 6 months blood draw, provided with a new copy of the consent form, and told that they do not have to participate in the 6 month blood draw. If the six-month blood draw is missed during the above outlined window, the study team may attempt to collect it for up to a year following the six-month timepoint.

Blood samples will be used to assess the immune response to SARS-CoV-2, drug screening, investigation of viral biology, cardiac biomarkers, and development of diagnostic assays. Plasma and peripheral blood mononuclear cells (PBMCs) will be stored in the University of Utah Center for Clinical and Translational Science (CCTS) biospecimen repository. If there is remaining sample after these analyses, they may be used to study other diseases.

Six months after enrollment, study staff will verify subsequent hospitalizations and vital status of the participant.

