5.4 Derived and Computed Variables

Definitions of Days For each subject, the day of randomization to treatment arm will be referred to as *DayR*. The day on which study drug is delivered is *DayD1*, with the next day being *DayD2* and so forth. The day 1 daily study assessment is referred to as occurring on *DayA1*; the next calendar day is *DayA2*, and so forth through *DayA15 = DayA1 + 14*. Note that if the baseline study assessment were to occur on the same calendar day as *DayA1*, the form name in the database will be used to distinguish in such instances which values are used for baseline values and which are used for *DayA1* values so that both sets of measurements can still be utilized. It is expected that for most subjects study drug will be delivered one day after randomization, i.e., that *DayD1 = DayR + 1*. It is also expected that for most subjects *DayD1 = DayA1*. However, because these relationships are not guaranteed, separate nomenclature is sometimes used to define outcomes (typically based on intervals beginning at *DayR*) and study assessments (often based on days since drug delivery or assessment day). Note that while 28-day symptom and quality of life assessments will be considered to be on *DayA28*, there is an allowed –2 day/+2 week window for when they occur. Likewise, the 6-month symptom and quality of life assessments for analysis purposes will use a –2 week/+2 month window. If a randomized subject never provides a daily assessment, such that the anchoring event for defining *DayA1* is unavailable, the convention will be taken to assume *DayA1 = DayR + 1*. Likewise, if study drug delivery date is not available, then it will be assumed that *DayD1 = DayR + 1*. Because swabs are intended to be delivered along with study drug, the drug delivery date will be assumed to correspond to swab delivery date, with the first swab to be collected on *DayD1*. There is likewise a window permitted for the Day 28 swab, although it is narrower: *DayR + 26 to DayR + 30, inclusive*.

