Participants may complete surveys late (e.g., slow response by email) or dates may be incorrectly entered that suggest assessments were done early. Additionally, surveys may be completed one day late by phone. It will be assumed that answers to any survey submitted 1 day before or after the intended day for the survey will be treated as the intended day. For example, if the day 4 and day 5 assessments are each completed by email four days after *DayD1*, it will be assumed that the day 4 responses pertain to *DayD4* and the day 5 responses pertain to *DayD5*. However, surveys submitted more than one day before or after the intended day will not be analyzed (except for baseline surveys, which have a longer window because they may be done any day between randomization and the study treatment delivery, inclusive, day 28 surveys, which have a -2 days/ $+2$ weeks window, and 6 month surveys, with a window of -2 weeks/ $+2$ months). Swabs will be analyzed based on the collection date reported by the participant, which may not necessarily match the day on the swab label. If multiple swabs from a participant have the same participant-reported collection date but different results, a positive result will supersede a negative result, and a negative result will supersede an invalid or indeterminate result. If collected swab dates are clearly erroneous (e.g., before day of randomization), the associated swabs will be ignored. If a swab was collected within ± 2 days of *DayR* $+ 28$, it will be regarded as a Day 28 swab.

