7.4.5 Quality of life (EQ-5D-5L Assessment)

The EQ-5D-5L quality of life assessment is administered at baseline, 28 days, and 6 months and we will analyze the VAS and an index measure, as described in Section 5.4. Multiple imputation of missing values will be implemented prior to analysis to improve inference given the expectation that missingness may depend on other characteristics. Imputation will include a death indicator for subjects who were known to have died before the assessment was to have occurred. After imputation, differences between day 28 (6 months) and baseline values of the VAS will be calculated. Any subjects whose measurement at day 28 (6 months) is missing because the individual died will then be post-processed to have a value worse than the worst possible difference among survivors (i.e., -101). Mean differences between day 28 (month 6) values and baseline will be compared between arms using a suitable approach (e.g., Van Elteren test), while adjusting for age stratum.

A similar analytical approach will be taken for the EQ-5D-5L index measure, except that the index measure will be set to 0 for individuals who were missing the assessment because they were deceased. No other missing index measure values will be imputed. Note that survivors may have a lower value for this index measure (i.e., <0) than those who are deceased.

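### Six-month surveys collected after the window have no stated use, and the EQ-5D-5L index is left as complete case for survivors while known deaths are kept at 0

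*Protocol*

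**What the plan says.** **Collection.** Protocol 5.5 schedules the six-month EQ-5D-5L, PHQ-9, GAD-7 and PTSD checklist with a window of -1 week/+2 months, and then adds: "If the six-month survey is missed during the above outlined window, the study team may attempt to collect it for up to a year" following that timepoint.

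**Analysis window.** SAP 5.4 states that "the 6-month symptom and quality of life assessments for analysis purposes will use a" -2 week/+2 month window. Its general rule is that "surveys submitted more than one day before or after the intended day will not be analyzed". The exceptions include "6 month surveys, with a window of" -2 weeks/+2 months. The current SAP text does not mention the extended collection period.

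**Missing values.** For the VAS, SAP 7.4.5 says "Multiple imputation of missing values will be implemented prior to analysis to improve inference", and the reason given is that missingness may depend on other characteristics. Deaths are then given a change score worse than any survivor could have. SAP 7.4.6 to 7.4.8 handle the PHQ-9, GAD-7 and PCL-5 totals in the same way. For the EQ-5D-5L index, people known to have died are set to 0 and then "No other missing index measure values will be imputed".

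**Status.** SAP 2.1.4 lists all of these as exploratory outcomes. SAP 1.2 allows further analyses that the SAP does not list, if reports identify them as unplanned.

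**The concern.** There are two gaps. First, the trial may ask participants for a questionnaire that the SAP does not say how to use. If its use is chosen after results are seen, that choice is open to question. Late responders are also the only six-month non-responders with any later score, so they offer a limited check on the missing-at-random assumption behind the imputation.

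Second, two summaries of one instrument are treated in opposite ways. The SAP's reason for imputing the VAS applies equally to the index. Under the index rule, a survivor who does not answer leaves the comparison, while a participant known to have died stays in at 0. Deaths then carry more weight than their share of the randomized arm. If non-response differs between arms, so does the distortion.

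**Working it through.** **1. Windows on one time scale** (1 month = 30.44 days)

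- SAP window: 6 x 30.44 - 14 = day 169, to 8 x 30.44 = day 244 (month 8).
- Protocol late collection: to 18 x 30.44 = day 548 (month 18).
- So 10 of the 12 months after the timepoint can yield surveys with no planned analysis. The documents give no late-response rate, so the number affected cannot be computed.

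**2. Can the late score enter the six-month imputation model?**

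A late survey is sought only when the in-window one was missed. The data therefore hold (baseline, day 28, six-month) for some people and (baseline, day 28, late) for others, but never six-month and late together. The association between those two, given baseline and day 28, appears in neither part of the likelihood. Its coefficient cannot be estimated without an added assumption about correlation over time, so no precision gain is credited to late scores.

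**3. Cost of not imputing the index**

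The documents state no figure to reproduce. Let f be the share of survivors with a missing six-month index (assumed 0.10-0.30) and R2 the variance explained by baseline and day 28 (assumed 0.3-0.4). Relative to complete data, the variance of an arm mean is:

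- complete case: 1/(1 - f)
- imputed: 1 + [f/(1 - f)](1 - R2)

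The proportional reduction simplifies to f x R2.

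| f | Complete case | Imputed, R2 = 0.3 | Imputed, R2 = 0.4 | Reduction |
|---|---|---|---|---|
| 0.10 | 1.111 | 1.078 | 1.067 | 3-4% |
| 0.20 | 1.250 | 1.175 | 1.150 | 6-8% |
| 0.30 | 1.429 | 1.300 | 1.257 | 9-12% |

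The overall range is 0.10 x 0.3 = 3% to 0.30 x 0.4 = 12%. On the confidence-interval scale this is a narrowing of 1 - sqrt(0.97) = 1.5% to 1 - sqrt(0.88) = 6.2%. None of it depends on late surveys.

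**4. Over-representation of deaths**

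Let d be the share of an arm that died. With all deaths kept and a share f of survivors dropped, the proportion of deaths among those analyzed is d/[d + (1 - d)(1 - f)]. Dividing by d gives an inflation of 1/[1 - f(1 - d)], which approaches 1/(1 - f) when deaths are rare: at most 1.11, 1.25 and 1.43 for f = 0.10, 0.20 and 0.30. The effect on the mean also depends on d, which the documents do not give. It is small if few outpatients die.

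**5. What a late-score sensitivity analysis can show**

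Suppose everyone missing at six months answers late, and the late effect is r times the six-month effect. Pooling gains power over complete case only if (1 - f) + f r > sqrt(1 - f), that is, r > [sqrt(1 - f) - (1 - f)]/f. This threshold is 0.49 at f = 0.10, 0.47 at 0.20 and 0.46 at 0.30. Whenever r differs from 1, the pooled estimate is biased for six months. Late scores therefore belong in a labelled sensitivity analysis and not in the main one.

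**The case against.** The strongest reply is that the plan is sound as it stands. A survey taken between months 8 and 18 is not a six-month measurement, and a fixed analysis window is ordinary practice. That stands. A reader might infer that the SAP wastes observed data, or that it is wrong to withhold the late score from the imputation model. The documents support neither reading: the first treats a later time as six months, and the second needs a coefficient that the collection rule makes inestimable.

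A reader might also infer that late responders are dropped from the trial's patient-reported results. They are missing only from the six-month index comparison. They remain in the imputed VAS, PHQ-9, GAD-7 and PCL-5 analyses, and in the day-28 analyses. Nor do the documents show that any late survey exists, because the protocol only permits an attempt. The SAP's lower bound of -2 weeks against the protocol's -1 week is not a conflict either: the SAP's change log says the union of the windows is used.

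It can also be said that SAP 1.2 already permits extra labelled analyses, and that the change log for SAP version 1.4 shows it was written after the primary manuscript was drafted. Both are true. An edit now may have to be labelled post hoc, which limits its value. Neither point explains why the index is handled differently from the VAS, and the SAP gives no reason.

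**Conclusion.** The point holds as a minor one. The documents leave a gap between what may be collected (to about month 18) and what is analyzed (to about month 8), and the SAP should say what the later surveys are for. The more substantive weakness is the complete-case index. It runs against the SAP's own expectation about missingness, inflates the share of deaths among those analyzed by up to 1/(1 - f), and gives up about 3-12% in the variance of an arm mean.

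That range rests on assumed missingness of 10-30% and assumed explained variance of 0.3-0.4, neither of which is in the documents. It describes an arm mean of the six-month value, whereas SAP 7.4.5 compares changes from baseline, possibly by a Van Elteren test, so it shows scale only. The primary and secondary outcomes are untouched.

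**What to change.** 1. In SAP 7.4.5, multiply impute missing survivor index values from baseline, day 28 and the covariates used for the VAS, and then set deaths to 0. The section names only a death indicator for the VAS model, so the other covariates should be listed once for both measures. If the index is to stay complete case, give the reason.
2. In SAP 5.4, keep the -2 week/+2 month window for the main analysis and state that later surveys do not enter it. Report the number and timing of late surveys by arm.
3. In SAP 7.4.5 to 7.4.8, add one labelled sensitivity analysis that takes the late score as the six-month value, noting that it mixes a later time with non-response. Mark it post hoc if six-month results have been seen.

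The cost is a short SAP edit, one more variable to impute and one extra set of tables. The downside is that late scores reflect a later time, so agreement with the main result is reassuring, while disagreement cannot be put down to non-response alone.
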